Aim 2: To generate proof of concept evidence demonstrating ability to provide high fidelity CIMT+taVNS treatment in a home-based setting in 3 infants. *Rationale:* The strongest level of evidence exists for delivery of pediatric interventions in home-based settings. We need to show evidence that CIMT +taVNS can be delivered effectively in the home and not just in a research clinic. *Aim Specific Methods:* We will videotape CIMT therapy sessions while the therapist is delivering taVNS in the home with EMG triggered taVNS and randomly score 20% of weekly session for CIMT treatment fidelity with the published CIMT Fidelity Instrument. Home based fidelity will be completed with the last 3 participants.

Project Relevance: Home-based constraint induced movement therapy (CIMT) is the gold standard treatment to facilitate arm and hand recovery after pediatric stroke, but it requires a large investment of time and energy from therapists and the family. Non-invasive brain stimulation (taVNS) is a promising new technology that may amplify the treatment effect of

Title: Extending taVNS Paired with Infant CIMT into a Home-Based Setting: Technology

Development Requisite for a Randomized Trial

PI: [name]

therapy treatment. Combining home-based CIMT & taVNS may provide families a better return on investment in terms of their child's functional gains from therapy services. This technology development pilot project will address important system modifications to automate pairing of active movement with taVNS delivers. This automation is needed to decrease the burden of pairing taVNS with CIMT and increase likelihood of clinical translation into home-based settings

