- 1) Hydrogel electrodes are placed in front of tragus and inner tragus/cymba chonchae, securing the wires behind head with tape. taVNS unit is attached to the baby using Velcro cummerbund (Fig.1, 2).

Title: Extending taVNS Paired with Infant CIMT into a Home-Based Setting: Technology Development Requisite for a Randomized Trial

PI: [name]

- 2) EMG electrodes will be placed on the shoulder (biceps/deltoid m) and on the trunk (paraspinus m) and connected to the taVNS unit via a wired interface.
- 3) CIMT and BSL therapists establish perceptual threshold (PT) daily, increasing slowly, until infant shows signs of tingling sensation. TaVNS is delivered at $0.1\text{mA} < \text{PT}$, $500\mu\text{sec}$, 25Hz, during each CIMT session, timed with movements of the weaker arm /trunk.
- 4) A CIMT therapist will deliver CIMT and use the manual trigger if needed for hand movements, while a second 'recording' therapist will record the active movement time. The Data Acquisition (DAQ) interface will record the amount of stimulation time and intensity from both EMG and manual triggering.
- 5) Good, moderate or poor impedance is constantly displayed on the taVNS unit. With poor contact, a beep sounds, and the electrode is adjusted.
- 6) Parent and OT will answer weekly questionnaire to assess their perception of ease of use, infant tolerance, and any recommendations for improvement of taVNS system or delivery.

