4.0 Study Endpoints

Primary Research Question: Can taVNS stimulation be automatically triggered during 75% of the total time for active infant arm and trunk movements during CIMT? **Primary Outcome measure:** Percentage of treatment sessions where total stimulation time was 75% of total active movement time.

Limitations and alternative approaches: *Trialing EMG system:* We will trial the EMG sensor system first with two healthy infants in the CHP laboratory setting to trouble shoot set-up and connection issues. The BSL and CIMT team will make any necessary modifications to the EMG-taVNS set-up. *Comparing total movement time to total stimulation time does not ensure stimulation is being provided at the appropriate time:* The stimulation device changes color when stimulation is being provided. Therefore, a second 'recording' therapist can monitor if the screen is green('on') when also recording active movement.

Aim 2: To generate proof of concept evidence demonstrating ability to provide high fidelity CIMT+taVNS treatment in a home-based setting in 3 infants. We will have a second therapist videotape CIMT therapy sessions while the CIMT therapist is delivering taVNS in the home with EMG triggered taVNS. We will randomly score 20% of sessions for CIMT treatment fidelity with published CIMT Fidelity tool. This aim will be completed with the final 3 participants after EMG set-up is finalized with first 2 participants.

Secondary CIMT+taVNS feasibility outcomes: Ability of therapist to operate taVNS easily and successfully by earning a "meet or exceed" score (3 or 4) on random therapy sessions by CIMT Fidelity Instrument. Ability of infant to tolerate wired ear electrode while remaining securely in place during sessions.

Secondary CIMT +taVNS efficacy outcomes: Change in the functional motor outcomes pre and post intervention on the *Quality of Upper Extremity Skills Test (QUEST)*

Title: Extending taVNS Paired with Infant CIMT into a Home-Based Setting: Technology Development Requisite for a Randomized Trial

PI: [name]

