10.0 Study Design / Methods

Title: Extending taVNS Paired with Infant CIMT into a Home-Based Setting: Technology

Development Requisite for a Randomized Trial

PI: [name]

Overall Study Design: The goal of this discovery pilot project is to further develop the technical aspects of taVNS+CIMT delivery so that it is practical for delivery by a CIMT therapist in a home-based setting. This is essential to prepare for a treatment effectiveness study, which by necessity must be home-based because of the minimum 40-hour time commitment. First, we will use EMG sensors to automatically trigger the taVNS device, with the goal of decreasing the burden of treatment for the therapist. We will place the EMG sensors on major muscle groups on the shoulder and trunk and refine placement as needed to show that EMG-triggering can accurately and effectively trigger stimulation for 75% of total time spent in active movements. The therapist will still be able to manually trigger for other targeted behaviors (such as grasping). Once our placement of sensors has been tested and meets this designated threshold, the EMG-triggered system will be tested in home-based CIMT treatment.

This study will determine the feasibility of using EMG sensors to trigger taVNS stimulation paired with CIMT therapy in n=5, 6-18month old infants with hemiplegia after perinatally acquired brain injury. We will measure the effect of active taVNS paired with 40 hours of CIMT on infant motor skills before and after treatment over a month, and follow up the motor skills over 3 months. All infants will receive active taVNS treatment. CIMT treatment is a non-research procedure, and motor and developmental testing are non-research procedures. taVNS is a research procedure. CIMT sessions will be videotaped, to measure the fidelity of CIMT delivery while the therapist is delivering taVNS to determine feasibility.

The alternative treatment is the usual and customary occupational therapy services. If parents wish, they may pursue CIMT therapy with local therapists, but there are very few qualified therapists in the area. Also, although CIMT is considered a gold standard intervention, it is often not covered by insurance due to the time intensity required.

We will monitor for and mitigate following risks are present with this study: Risk of skin irritation, risk of discomfort, risk of slightly decreased heart rate, and risk of loss of confidentiality.

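### The outcome for operating taVNS is scored only on CIMT fidelity, so it cannot show that taVNS was operated successfully

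*Combined protocol and SAP*

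**What the plan says.** Section 4.0 lists as a secondary feasibility outcome "Ability of therapist to operate taVNS easily and successfully by earning a" score of 3 or 4 "on random therapy sessions by CIMT Fidelity Instrument". No other condition is attached: nothing on stimulation time, threshold setting, triggering or electrode contact. The plan does not say how many of the scored sessions must reach 3 or 4.

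The document describes what the instrument scores in three places:

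- Section 1.0, Aim 2: "randomly score 20% of weekly session for CIMT treatment fidelity with the published CIMT Fidelity Instrument".
- Section 4.0, Aim 2: "We will randomly score 20% of sessions for CIMT treatment fidelity with published CIMT Fidelity tool".
- Section 10.0, on the purpose of the videos: "to measure the fidelity of CIMT delivery while the therapist is delivering taVNS to determine feasibility".

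Other parts of the plan do concern taVNS delivery and ease of use. The primary outcome in Section 4.0 compares stimulation time with active movement time against a 75% mark. Section 3.0 (C2.1.2, item 4) has the DAQ interface record stimulation time and intensity. Item 6 of the same list says: "Parent and OT will answer weekly questionnaire to assess their perception of ease of use". None of these enters the success rule for the therapist's operation of taVNS.

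**The concern.** The outcome is named for one thing and measured by another. The name is about running the stimulator; the measure is about the quality of the therapy given alongside it. The two can move apart. Sections 2.0 and 3.0 describe manual triggering as a distraction and a mental load for the therapist, so attention to the device and attention to CIMT may compete.

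Aim 2 is to show that the combined treatment can be delivered with high fidelity at home, and the only scoring stated under that aim is of CIMT. Section 1.0 says the results will support a grant application for a randomised trial of home-delivered taVNS with CIMT. A statement in that application that therapists operated taVNS successfully at home would lack support if it rested on this score.

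**Working it through.** The plan gives no sample size, error rate or target proportion for this outcome, so there is no figure to reproduce. The check has two parts: how many sessions carry the outcome, and what the rule can and cannot tell apart.

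**Number of scored sessions**

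- Sessions per infant (Section 3.0, C2.1.2): 5 per week × 4 weeks = 20. This agrees with 40 h ÷ 2 h = 20.
- Infants in the home fidelity assessment (Section 1.0, Aim 2): 3.
- Home sessions: 3 × 20 = 60.
- Scored sessions: 0.20 × 60 = 12, that is 4 per infant, or one per week (0.20 × 5 = 1).

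**What the rule distinguishes**

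Cross the CIMT score with the plan's own delivery criterion, read as at least 75% in line with Aim 1 in Section 1.0:

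| CIMT score | Stimulation share of active movement time | Current rule for operating taVNS |
|---|---|---|
| 3 or 4 | 75% or more | success |
| 3 or 4 | below 75% | success |
| below 3 | 75% or more | not success |
| below 3 | below 75% | not success |

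The result depends only on the first column. The rule gives the same answer whatever happened with stimulation.

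**What the score does bear on**

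The name has two parts, ease and success. If CIMT quality is preserved while taVNS is running, the device is not getting in the therapist's way. That is indirect evidence on ease, and it matches the purpose given in Section 10.0. It is not evidence that stimulation was set up, triggered and delivered as intended.

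**What planned data could bear on success**

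- Stimulation time and intensity are recorded by the DAQ interface (Section 3.0, C2.1.2, item 4). That item says the record covers EMG and manual triggering. It does not say the two are stored separately.
- Active movement time is assigned to a recording therapist in the same item. For home sessions, Section 4.0 has the second therapist videotaping, and Sections 6.0 & 7.0 have the second team member assisting, videotaping and monitoring. Neither mentions recording active movement time at home.
- Ease of use is covered by the weekly questionnaire (item 6), for which no scale or threshold is given.
- Electrode contact is displayed, with an audible alert when poor (item 5). Nothing says that alerts are logged or counted.

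**The case against.** The strongest reply is that poor delivery is caught elsewhere. The primary outcome compares stimulation with active movement session by session, nothing in Section 4.0 limits it to the lab infants, and the DAQ record feeds it. This stands: low stimulation in the home sessions would not go unseen in the trial. It does not repair this outcome, because nothing ties the primary result to the scored sessions or says how to read the two results if they disagree.

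A second reply is that the score has a sensible rationale. The known difficulty is that triggering distracts the therapist, so preserved CIMT quality is a fair functional test. A therapist with weaker CIMT should also fall short of Aim 2, since high-fidelity CIMT is part of its target. Both points stand, and they are why the measure should be kept under a name that fits it.

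A reader might go further and infer that a therapist could ignore the device, deliver almost no stimulation and still have the trial report complete success. The documents do not support that as a realistic picture. Stimulation is mainly EMG-triggered, with manual triggering for hand movements. Poor contact sounds an alert and the electrode is adjusted. A second team member attends home sessions, and the move to the home follows a 75% check in the first two infants. Twelve passes with little stimulation is a logical possibility under this one rule, not an estimate of what would happen.

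Finally, the instrument's items are not reproduced and some pages were not available for review. A taVNS item is therefore possible, though every description given is of CIMT fidelity.

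**Conclusion.** The point holds in a limited form. As written, the outcome can report that taVNS was operated successfully without containing evidence that it was. Its reach is one secondary feasibility outcome, resting on about 12 scored sessions in 3 infants, and the Aim 2 conclusion drawn from it. The primary outcome is untouched, and no hypothesis test or stopping rule depends on this score. The correction is still worth making because it changes what Aim 2 can claim.

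This rests on three assumptions: that the instrument scores CIMT fidelity only, as the document consistently describes it; that scoring covers the three home infants, each with 20 sessions; and that 20% is applied evenly. If the instrument does contain taVNS items, the sponsor can answer the point by listing them and saying how they enter the score.

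**What to change.** In Section 4.0:

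1. Rename the existing measure CIMT fidelity during taVNS, reported as the share of scored sessions at 3 or 4.
2. Report taVNS operation separately for the home sessions, from planned data: DAQ stimulation time relative to recorded active movement time, using the existing 75% criterion, and the therapist's weekly ease-of-use questionnaire.
3. Base the Aim 2 statement on high-fidelity combined treatment on both results together.

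The sponsor should confirm that active movement time is recorded in home sessions and by whom, since the second person's stated duties there do not include it. Report the manual-trigger share only if the DAQ interface stores it separately. Do not rely on counts of poor-contact alerts, which the protocol does not say are logged.

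The cost is endpoint wording and some tabulation. If active movement time is not currently planned for home sessions, recording it would be an addition. The success figure may become less favourable, because CIMT quality alone would no longer be enough to support the Aim 2 statement.

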5.0 Inclusion and Exclusion Criteria/ Study Population

Inclusion Criteria: Five 6–18 month-old infants, with hemiplegia/motor asymmetry qualifying for CIMT, Gross Motor Function Classification System (GMFCS) level I-IV, ability to maintain sitting position for 5 minutes with moderate assistance.

Exclusion Criteria: GMFCS level V, severe motor impairment/ quadriplegic involvement; uncorrected blindness or deafness, cardiomyopathy.

6.0 & 7.0 Number of Subjects and Setting

We will enroll up to 5 infants. The first two infants will complete all study intervention procedures in the pediatric occupational therapy lab ([name]). This will allow for monitoring by the whole team and minor modifications to be made to the set-up (adjusting placement of EMG sensors, adding Velcro to keep wires out of the way when reaching, etc). Image from on-going taVNS +CIMT study (without EMG triggering).

This new study should only require minor changes to the set-up (adding wires for EMG muscle sensors). After completing 2 infants in the lab which should provide more than enough opportunity to modify set-up issues. The remaining 3 participants will complete study interventions in their home. A specially trained pediatric therapist will deliver all treatment sessions. A second study team member will also accompany the therapist to assist with therapy, video tape sessions, and monitor the infant.

Figures 1 & 2. CIMT therapist assists infant's trunk control while the trigger button is attached to her hand with flexible wrap (red arrow). taVNS device is Velcro attached to the infant's back (green arrow). The arm with better motor skill is immobilized with red flexible wrap and a splint.

8.0 Recruitment Methods

We have IRB approval for two pilot studies (#67997, #103800) in preterm and term stroke/HIE infants with taVNS paired with feeding using similar taVNS study procedures as proposed in this application. The taVNS system has a non-significant risk device designation from MUSC's IRB in these two pilot trials.

[name] will screen for infants in the nursery with known brain injury that will likely lead to hemiparesis or weakness, such as perinatal arterial stroke, HIE, severe IVH, PVL or cerebellar infarct, regardless of sex or race. The clinical team will inform the parents of the potential to

Title: Extending taVNS Paired with Infant CIMT into a Home-Based Setting: Technology

Development Requisite for a Randomized Trial

PI: [name]

participate in the study. [name] will then explain the study to the parents and give them contact information if they are interested, to initiate screening and consent procedures when their infant reaches 6-8months of age. Infants are also referred directly to [name] and [name] specifically for CIMT from a wide region of the southeast. Because some parents travel great distances to get these services, we may obtain referrals from other care providers out of our region. We will perform phone screening and obtain Econsent prior to patient arrival for patients whose parents cannot meet in person prior to the first treatment session, to be able to get services fully prepared for the visit. We will use the approved REDcap system to obtain consent. [name] or other approved study personnel will go over the entire consent document on the phone with the parent to ensure comprehension and to confirm identity. Parent will be given a copy of the completed, signed consent form in person or by email or fax.

Volunteers of all ethnicities and racial categories will be accepted into this study protocol. No preference will be given based on race, gender or ethnicity. Young infants who had perinatal complications leading to perinatally acquired brain injury may be considered vulnerable populations and are the target of this proposal.

The parents of infants who present for CIMT are highly motivated, and willing to commit to the time and effort commitment for CIMT. Most of the study procedures occur during the active treatment period. Therefore, we anticipate >95% retention to completion of the immediate outcome measures. For the 3 months follow-up assessment, we will call every month to discuss infant progress with the mother/caregiver. All of these infants will also have regular developmental follow-up in MUSC's or other high-risk clinic, and we will collect this data with parent consent, though it is not part of the primary or secondary outcomes for the phase I trial.

9.0 Consent Process

Drs. [name], [name], or [name] (PI and Co-Investigators) will explain the study to these parents by phone or conference call and obtain written informed consent when they and their infants present to the Occupational therapy department for CIMT. Based on our 87% consent rate in the pilot taVNS-feeding study, and the ready parental acceptance of taVNS, we anticipate no significant parental concerns that would impact enrollment. We will not have a Spanish language consent.

We will perform phone screening and obtain eConsent prior to patient arrival for patients whose parents cannot meet in person prior to the first treatment session, to be able to get services fully prepared for the visit. We will use the approved REDcap system to obtain consent. [name] or other approved study personnel will go over the entire consent document on the phone with the parent to ensure comprehension and to confirm identity. Parent will be given a copy of the completed, signed consent form in person or by email or fax.

10.0 Study Design / Methods

Title: Extending taVNS Paired with Infant CIMT into a Home-Based Setting: Technology

Development Requisite for a Randomized Trial

PI: [name]

Overall Study Design: The goal of this discovery pilot project is to further develop the technical aspects of taVNS+CIMT delivery so that it is practical for delivery by a CIMT therapist in a home-based setting. This is essential to prepare for a treatment effectiveness study, which by necessity must be home-based because of the minimum 40-hour time commitment. First, we will use EMG sensors to automatically trigger the taVNS device, with the goal of decreasing the burden of treatment for the therapist. We will place the EMG sensors on major muscle groups on the shoulder and trunk and refine placement as needed to show that EMG-triggering can accurately and effectively trigger stimulation for 75% of total time spent in active movements. The therapist will still be able to manually trigger for other targeted behaviors (such as grasping). Once our placement of sensors has been tested and meets this designated threshold, the EMG-triggered system will be tested in home-based CIMT treatment.

This study will determine the feasibility of using EMG sensors to trigger taVNS stimulation paired with CIMT therapy in n=5, 6-18month old infants with hemiplegia after perinatally acquired brain injury. We will measure the effect of active taVNS paired with 40 hours of CIMT on infant motor skills before and after treatment over a month, and follow up the motor skills over 3 months. All infants will receive active taVNS treatment. CIMT treatment is a non-research procedure, and motor and developmental testing are non-research procedures. taVNS is a research procedure. CIMT sessions will be videotaped, to measure the fidelity of CIMT delivery while the therapist is delivering taVNS to determine feasibility.

The alternative treatment is the usual and customary occupational therapy services. If parents wish, they may pursue CIMT therapy with local therapists, but there are very few qualified therapists in the area. Also, although CIMT is considered a gold standard intervention, it is often not covered by insurance due to the time intensity required.

We will monitor for and mitigate following risks are present with this study: Risk of skin irritation, risk of discomfort, risk of slightly decreased heart rate, and risk of loss of confidentiality.

Risk of skin irritation: we will monitor the skin on the inner aspect of the left ear before and after each session, and will switch to the right ear if redness is present, and decrease the stimulation if redness persists.

Risk of discomfort: We will protect against the risk of discomfort by close monitoring. We will use the mother's perception of infant discomfort and infant signs of discomfort to determine the perceptual threshold, and then treat at 0.1mA less than this level of perception. If any infant seems to be in discomfort during the CIMT taVNS session, we will decrease the microcurrent by 0.1mA, as in our feeding taVNS trial in infants. We will use facial expression change, fidgety movements and infant vocalization as signs of behavioral discomfort, to indicate need for decreasing the microcurrent during the taVNS session.

Title: Extending taVNS Paired with Infant CIMT into a Home-Based Setting: Technology

Development Requisite for a Randomized Trial

PI: [name]

We will not continuously monitor heart rate during the taVNS session, as our extensive HR data in infants show no bradycardia and no decrease in HR beyond 60 seconds after starting stimulation.

Risk of loss of confidentiality: We will check the infant's medical records to gather the following information: gestational age at birth, ventilator support, head ultrasound and MRI results, bottle feeding, infection, neonatal condition during labor and delivery, infant's treatments and conditions, and developmental progress.

We will assign study numbers to each participant, keep CRF and consent forms in locked offices. Database files with names and contact information will be password protected and stored on the MUSC Pediatric server. All other data files related to this study will be identified by participant number only, without link to standard identifiers. We will publish the aggregate data only.

